 proposed methodology described below. Assumptions regarding responder analyses include the following: If the subject does not meet the criteria of either pain or function at either Visit 6 or Visit 8, the subject will be considered a non-responder. If the subject meets the pain and function improvement criteria at both Visit 6 and Visit 8, and has no post-treatment intervention as of the date of Visit 8, the subject will be considered a responder. Any subject that is a non-responder on one of the two primary study visits (Visit 6 or Visit 8) but has a missing outcome for the other study visit is deemed a non-responder and not considered to have a missing outcome for the primary analysis. If a subject does not have a minimum of a visit at 3-months (Study Visit 4) they will be considered a non-responder. Any subject that has a minimum of 3-months data (Study Visit 4) but is missing one or both of the two primary study visits, will have their outcome multiply imputed based on their available information. Separate models will be constructed for Subjects that are missing one of the two primary study visits.

A detailed description of the statistical methodology for multiple imputation of missing data for responder analyses can be found in the SAP.
For subjects who have a post-treatment interventional procedure at the treated level, the analyses of continuous and categorical efficacy variables will include only data collected before the post-treatment adjudicated intervention.
MMRM will be used for the analysis of over time of quantitative variables and missing data will not be imputed.
Examination of Subgroups Pre-specified subgroup analyses based on both the ITT and PP analysis sets for the primary and secondary efficacy variables will be performed for key demographic and baseline variables, as described in the SAP.

TABLE OF CONTENTS

IN	VESTI	GATOR	'S SIGNATURE	2
PR	отос	COL SYN	NOPSIS	3
LIS	ST OF	TABLE	S	41
LIS	ST OF	FIGUR	ES	41
LIS	ST OF	APPEN	DICES	41
GL	OSSA	RY OF A	ABBREVIATIONS	43
1.	BAC	KGROU	ND	46
	1.1	Degene	erative Disc Disease and Low Back Pain	46
	1.2	Curren	t Treatment Options for Low Back Pain	47
				48
				49
				50
				51
				52
				53
	1.6	Study I	Rationale	
		1.6.1	Rationale for the Study	
		1.6.2	Rationale for Study Design	
		1.6.3	Rationale for Dosing Regimen and Treatment Period	
	1.7	Risk/B	enefit Summary	
		1.7.1	Reaction to Dimethyl Sulfoxide	60
		1.7.2	Potential Cell Contamination	60
		1.7.3	Tumor Development	61

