4.5 Subject Withdrawal

Subjects will be free to withdraw from the study at any time, for any reason.

A subject also may be withdrawn/removed by the investigator, if necessary, to protect the subject's health. The investigator has the right to withdraw subjects from the study in the event of intercurrent illness, adverse events, administrative, or other reasons. Any reasons for withdrawal must be documented and explained to the subject.

It is understood, however, by all concerned, that an excessive rate of withdrawals can render the study uninterpretable. Therefore, unnecessary withdrawal of subjects should be avoided.

If for any reason a treated subject is withdrawn from study participation, the reason for and date of withdrawal from the study must be recorded. If the reason for withdrawal is an adverse event or a clinically significant abnormal laboratory test result, monitoring will continue until the event has resolved, stabilized, or until the follow-up period is complete.

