9.7.1 Primary Safety Endpoint

Evaluation of overall safety, which includes the following:

- Subject reported AEs and SAEs from baseline through 24 months post-treatment, including adverse events of special interest (i.e., AEs of worsening low back pain)
- Laboratory tests (hematology, serum chemistry, inflammatory markers and antibody analysis). Abnormal results will be assessed relative to normative ranges and shift tables from baseline through 24 months post-treatment
- Reported events from radiographic imaging from baseline through 24 months posttreatment, including disc height at the treated level
- Post-treatment interventions affecting the treated disc through Visit 8 (24 months posttreatment) (comparison of the proportion of subjects in each group with an adjudicated post-treatment intervention at the treated level, and the proportion of subjects in each group with an adjudicated post-treatment intervention any lumbar level)
- Vital signs (heart rate, blood pressure and temperature) and body measurements (height, weight and BMI)
- Physical examinations (abbreviated).
- Neurological examinations (motor, sensory, reflex).

[figure not shown]
Descriptive statistics will be used for the summary of safety parameters – the number and percentage will be used for the incidences of AE/SAEs, deaths, early discontinuation due to AEs, and post-treatment interventions. The AE/SAE severity and relationship with the study procedure and treatment will be summarized and presented.

The mean, standard deviation/error, minimum, median, and maximum will be used for the laboratory parameters. The shift table (cross-tabulation) for the changes from baseline (low/normal/high) for the laboratory parameters will also be also provided and the test for treatment difference.

[figure not shown]
Safety parameters of special interest (i.e., AEs of worsening low back pain) will be summarized through 24 months post-treatment by treatment arm, severity, and the time from the study injection to the start of the AEs (0 to \leq 7 days, >7 days to < 3 months, \geq 3 months to 24 Months).

The incidence of this special interest AE (worsening low back pain) occurring within 3 to 24 months after study treatment will be also summarized, by treatment arm, for the responders and non-responders of the Primary Efficacy Endpoint.

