9.9 Handling of Missing Values, Early Termination, or Non-Interpretable Data

For the responder analyses, including the primary efficacy endpoint, as well as pain and function responder analyses, subjects will be classified as having attained success (responder) or not attained success (non-responder).

The Primary Efficacy Endpoint requires a subject to meet clinically significant improvements in both pain and function at both 12 and 24 months, as well as not undergo any post-treatment intervention at the treated level through 24 months, to be considered a success.

If in-clinic assessments for Study Visits 6 and 8 (corresponding to 12 and 24 months) are unavailable, the data will be considered missing. If a scheduled in-clinic visit is missed, the site should contact the subject to determine if any interventions that would classify the subject as a treatment failure have occurred since their last visit. If any interventions are reported, the site should collect all the information required if the intervention had been reported at an in-clinic visit. All intervention information collected remotely must be documented in a source document and/or worksheet.

If a subject receives a post-treatment intervention at the treated level on or prior to the date of Study Visit 8 (24 months), this subject will be considered a non-responder regardless if there is any missing data. For example, a subject that has a post-treatment intervention at the treated level at the time of Study Visit 4 (3 months) would be considered a non-responder regardless of whether there are Visit 6 or Visit 8 data available for analysis, as they would have already failed one of the criteria to be considered a responder.

If a subject has data available at both Study Visit 6 (12 months) and Study Visit 8 (24 months), with no post-treatment intervention at the treated level as of the date of Study Visit 8, that subject will be determined either a responder or non-responder based upon whether or not the subjects meets the pain and functional improvement criteria at both study visits.

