Any subject that is missing one or more components in an endpoint (e.g. VAS in the primary endpoint) at a visit will be considered a non-responder at that visit if any available component of the endpoint indicates that the subject is a non-responder (even if all components of the endpoint are not available). If none of the available components impose non-response, the outcome will be considered missing and will be handled according to the proposed methodology described below.

Assumptions regarding responder analyses include the following:

- If the subject does not meet the criteria of either pain or function at either Visit 6 or Visit 8, the subject will be considered a non-responder.
- If the subject meets the pain and function improvement criteria at both Visit 6 and Visit 8, and has no post-treatment intervention as of the date of Visit 8, the subject will be considered a responder.

- Any subject that is a non-responder on one of the two primary study visits (Visit 6 or Visit 8) but has a missing outcome for the other study visit is deemed a non-responder and not considered to have a missing outcome for the primary analysis.
- If a subject does not have a minimum of a visit at 3-months (Study Visit 4) they will be considered a non-responder.
- Any subject that has a minimum of 3-months data (Study Visit 4) but is missing one or both of the two primary study visits, will have their outcome multiply imputed based on their available information. Separate models will be constructed for
 - Subjects that are missing one of the two primary study visits (Visit 6 or Visit 8) but not both;
 - \circ Subjects that are missing both of the primary study visits.

A detailed description of the statistical methodology for multiple imputation of missing data for responder analyses can be found in the SAP.

For subjects who have a post-treatment interventional procedure at the treated level, the analyses of continuous and categorical efficacy variables will include only data collected before the post-treatment adjudicated intervention.

MMRM will be used for the analysis of over time of quantitative variables and missing data will not be imputed.

The SAP provides additional details regarding methods for handling missing data.

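### A subject who dies after Month 3 can be imputed as a 12-and-24-month responder, and no visible sensitivity analysis tests the imputation of withdrawals for harm or lack of efficacy

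*Combined protocol and SAP*

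**What the plan says.** The primary endpoint (Section 9.4.1) needs a fall of 50% or more in low back pain VAS and of 15 points or more in ODI at both Visit 6 (Month 12) and Visit 8 (Month 24), with no intervention at the treated level.

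Section 9.9, with the same rules in the synopsis, deals with incomplete data as follows:

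- Intervention at the treated level by the date of Visit 8: non-responder, whatever else is missing.
- Incomplete components at a visit: the subject is "considered a non-responder at that visit if any available component of the endpoint indicates that the subject is a non-responder".
- One primary visit failed and the other missing: the subject is "deemed a non-responder and not considered to have a missing outcome for the primary analysis".
- No Month 3 visit: "If a subject does not have a minimum of a visit at 3-months (Study Visit 4) they will be considered a non-responder".
- Otherwise, a subject who has Month 3 data but "is missing one or both of the two primary study visits, will have their outcome multiply imputed based on their available information".

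An in-clinic assessment that is unavailable at Visit 6 or 8 is treated as missing, without regard to why. The reasons are collected elsewhere. Section 4.5 requires that "the reason for and date of withdrawal from the study must be recorded", and Section 9.7.1 summarises "incidences of AE/SAEs, deaths, early discontinuation due to AEs, and post-treatment interventions". No responder rule refers to either. Section 9.9 leaves the detailed imputation method to the SAP, and that text is not among the documents reviewed. Section 9.3.2 names the sensitivity analyses for efficacy: repeats on the Full Analysis Set, the As Treated set and the Per Protocol set.

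**The concern.** A subject who has died has no 24-month VAS or ODI. That value does not exist, so it is not missing in the sense that imputation assumes, and the subject cannot have met an endpoint that requires success at Month 24. Yet the rule lets a subject who dies at Month 6 be drawn as a success.

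For withdrawals the issue is one of assumption. Imputing from a subject's available data supposes that those who left would have done as well as similar subjects who stayed. That is least secure for subjects who leave because the treatment did not work or because of an adverse event. If such losses differ between arms, the arm with more of them is credited with more imputed responders, and its posterior probability moves with them. Section 9.9 applies its rules to the responder analyses generally, so the responder endpoints in the secondary hierarchy inherit the same handling.

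**Working it through.** **Step 1: trace the rules by case.**

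| Subject | Outcome under Section 9.9 |
|---|---|
| Dies or withdraws before Visit 4 | Non-responder |
| Lost after Visit 4, treated-level intervention by Visit 8 | Non-responder |
| Lost after failing pain or function at Month 12 | Non-responder |
| Lost between Months 3 and 12, no intervention (including death, adverse event, lack of efficacy) | Imputed |
| Succeeded at Month 12, lost before Month 24, no intervention (including death) | Imputed |

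The point concerns the last two rows. Nothing visible sets the chance of success to zero there, even for a death.

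**Step 2: look for an analysis that would expose it.** Section 9.3.2 changes only who is analysed. Section 6.2 refers to a last-observation-carried-forward analysis described in Section 9.9, but Section 9.9 contains none. No non-responder or tipping-point analysis is visible.

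**Step 3: reproduce the plan's figures.** Arm size: 360 / 3 = 120 (Section 9.2). Threshold for two comparisons at family-wise one-sided 0.025: 1 − 0.025/2 = 0.9875. This matches Section 9.6.3, which states it for the secondary endpoints; the primary value is left to the SAP.

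**Step 4: responders affected per arm.** All inputs are assumed: 2% to 6% of an arm falls in the last two rows through death, an adverse event or lack of efficacy, and the imputed response is 15% to 40%.

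- Low: 120 × 0.02 × 0.15 = 0.36 responders, or 0.36/120 = 0.3 points.
- High: 120 × 0.06 × 0.40 = 2.88 responders, or 2.88/120 = 2.4 points.

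**Step 5: bias in the difference.** With 6% such losses in an active arm, 2% in saline, and a common imputed response of 20% to 30%: (0.06 − 0.02) × 0.20 = 0.8 points, and (0.06 − 0.02) × 0.30 = 1.2 points, in favour of the active arm. Reversing the shares gives −0.8 to −1.2.

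**Step 6: effect on the test.** This is an illustration with 40 v 25 observed responders of 120, Beta(0.5, 0.5) priors (Section 9.6.2) and 400,000 draws. Lost subjects are imputed at their own arm's rate among the rest; with 12 v 4 losses the rates are 40/108 = 0.370 and 25/116 = 0.216.

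| Handling of these losses (active v saline) | Posterior probability |
|---|---|
| All non-responders | 0.9858 |
| Imputed, 6 v 6 | 0.9863 |
| Imputed, 12 v 12 | 0.9875 |
| Imputed, 12 v 4 | 0.9949 |
| Imputed, 4 v 12 | 0.9703 |

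The simulation error is about √(0.9875 × 0.0125 / 400,000) = 0.0002, so the 12 v 12 result cannot be placed on either side of 0.9875. Two limits apply. The example was set just below the threshold, and 12 v 4 is 10% v 3.3%, a wider imbalance than in Step 5.

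**The case against.** The strongest objection is that the decisive text is absent. The SAP may classify deaths, or use the reason for withdrawal in its model. That stands as a limit on what can be concluded. But the protocol states its rule without condition, so if the SAP does make an exception, the protocol needs aligning with it.

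Second, much failure is already captured. A reader might infer that every subject lost after Month 3 is imputed, or that known treatment failures count as successes. The documents do not support either reading. Section 12.2.1 uses treatment failure for an adjudicated intervention at the treated level, which is always non-response, and so is an observed failure at Visit 6 or 8. Sites must also ask about interventions after a missed visit (Section 6.3).

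Third, imputation uses the subject's available information, and Section 4.6 seeks end-of-study assessments at withdrawal where possible. A poor exit score may lower the imputed chance of success. This is fair, and it means that the 15% to 40% range could be too high for those who leave in pain. It does not bring the chance to zero, and it does not help with a death.

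Fourth, Visit 4 can be read as a minimum-data condition for imputation, and any cut-off separates neighbouring cases. That is reasonable for ordinary missing data, but not for deaths, whose 24-month status is the same on either side of the cut-off.

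Finally, coding withdrawals for adverse events or lack of efficacy as failures in the primary analysis is a choice of estimand on which statisticians differ. A withdrawal for an adverse event does not show that VAS or ODI failed. This objection stands, and for that reason those withdrawals belong in a sensitivity analysis here.

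**Conclusion.** The point holds for two groups: subjects lost between Months 3 and 12 without an intervention, and subjects who succeed at Month 12 and are lost before Month 24. Among them, deaths are handled wrongly by the rule as written. Withdrawals for an adverse event or lack of efficacy are handled in a defensible way that no visible analysis tests.

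The size cannot be established, since every loss rate and imputed response above is assumed. The figures also cover deaths and withdrawals together. Deaths alone should be rare, so reclassifying them should change the primary result little; the sensitivity analysis addresses the larger share. A reader might infer that the rule favours the active arms. The documents give no basis for a direction: the bias follows whichever arm has more such losses.

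**What to change.** 1. In the synopsis and Section 9.9, ahead of the imputation bullet, state that a subject who dies before Visit 8 is a non-responder for the primary and all responder endpoints. Align the SAP's detailed imputation text with this, or confirm that it already agrees.
2. Pre-specify a sensitivity analysis of the primary endpoint that codes as non-responders all withdrawals for lack of efficacy, worsening back pain, or an adverse event related to product or procedure. Classify the reasons blind to treatment before database lock.

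No new data are needed, since reasons for withdrawal and deaths are already recorded. The cost is a sentence in each place, one extra analysis, a blinded classification of reasons, and slightly lower response rates.

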DCSI	Development Core Safety Information (document)
DMC	Data Monitoring Committee
DMSO	Dimethyl sulfoxide
DSMB	Data Safety Monitoring Board
EAC	Events Adjudication Committee
EC	Ethics Committee
ECG	Electrocardiogram
eCRF	Electronic case report form(s)

GLOSSARY OF ABBREVIATIONS

EDC	Electronic data capture
EEA	European Economic Area
EOT	End of Treatment
eGFR	Estimated glomerular filtration rate
eform	Electronic form (page)
EU	European Union
FAS	Full analysis set
FDA	Food and Drug Administration
FSH	Follicle stimulating hormone
γ-GT	Gamma-glutamyl transpeptidase
GCP	Good clinical practice
GFR	Glomerular filtration rate
HA	Hyaluronic acid
HbA1c	Glycosylated hemoglobin
Hct	Hematocrit
HDL	High density lipoprotein
HIPAA	Health Insurance Portability and Accountability Act
HLA	Human leukocyte antigen
HR	Heart Rate
hsCRP	High sensitivity C-reactive protein
IB	Investigator's Brochure
ICD	Implantable Cardioverter Defibrillator
ICH	International Conference on Harmonization
IEC	Independent Ethics Committee
IL	Interleukin
IP	Investigational product
IND	Investigational New Drug
INN	International Non-Proprietary Name
iPCQ	iMTA Productivity and Cost Questionnaire
IRB	Institutional Review Board
ISF	Investigator's Study File
ITT	Intent to treat
IVD	Intervertebral disc
IVRS	Interactive voice response system
IWRS	Interactive web response system
LDH	Lactate dehydrogenase
LDL LOCE	Low density lipoprotein
LOCF MED	Last Observation Carried Forward
MED MPC	Morphine equivalent dose Mesenchymal precursor cells
	Mesenchymal precursor cells Modification of Diet in Renal Disease
MDRD mITT	Modified intent-to-treat

GLOSSARY OF ABBREVIATIONS

MedDRA	Medical Dictionary for Regulatory Activities
MORES	Male Osteoporosis Risk Estimation Score
MPC	Mesenchymal precursor cell
MRI	Magnetic resonance imaging
MSC	Mesenchymal stem cells
MTX	Methotrexate
NIH	National Institutes of Health
NSAID	Non-Steroidal Anti-inflammatory Drugs
NYHA	New York Heart Association
PFT	Pulmonary Function Testing
PHI	Personal health information
PP	Per protocol analysis set
PRA	Panel reactive antibody
PRP	Platelet-rich plasma
PT/INR	Prothrombin time/International normalized ratio
QSI	QMA [®] Stability Index
RANKL	Receptor Activator of Nuclear Factor Kappa-B Ligand
RBC	Red blood cell
RR	Respiratory rate
SAE	Serious adverse event
SAP	Statistical analysis plan
SAT	Self-assessment of Treatment (Questionnaire)
SBP	Systolic blood pressure
SEM	Standard Error of Mean
SMBG	Self-monitored blood glucose
SMT	Study Management Team
SPC SUGAD	Summary of Product Characteristics
SUSAR T2DM	Suspected Unexpected Serious Adverse Reaction
T2DM TG	Type 2 Diabetes Mellitus
TEC	Triglycerides Treatment Events Committee
ΤΕC TNF-α	Tumor necrosis factor-α
TPDR	Translation per degree rotation
ULN	Upper limit of normal
WBC	White blood cell

1. BACKGROUND

1.1 Degenerative Disc Disease and Low Back Pain

The degenerative process in the disc, unlike many other tissues begins as early as the second decade of life. ¹⁻⁶ Degeneration of the intervertebral disc(s), commonly referred to as Degenerative Disc Disease, is consistent with advancing age, and in many cases is also associated with pain (particularly in the lumbar spine)⁷ and biomechanical instability. ⁸⁻¹⁴ Currently, it is unknown what factors serve as an initiating event of painful degeneration, but genetic predisposition, smoking, infection, abnormal biomechanical loading, decreased nutrient transport across the vertebral endplates and ageing are implicated. ^{3,15,16}

Degenerative changes are believed to begin in the nucleus pulposus with cellular loss causing an imbalance in the anabolic to catabolic processes leading to net proteoglycan breakdown and the associated diminished water binding capacity. ^{10,15,17} This places abnormal compressive forces on the annulus fibrosus that cause damage resulting in cracks, tears and fissures. ^{9,12-14,18}

It has been hypothesized that an event secondary to a structural deficit, such as injury or leakage of nucleus pulposus material through annular fissures, is likely to result in recruitment of immune cells to the disc, which then triggers pain generation. ¹⁵ This is consistent with a theory that low back pain is associated with inflammation in the disc. ^{8,10,11, 15,16,19} As the annulus fibrosus begins to have more cracks and fissures, the inflammatory mediators come into contact with the nerves in the outer portion of the annulus potentially causing pain. ^{8,10,11, 15,16,19} This causes infiltration of immune cells, blood vessels and nerve fibers further into the disc in an attempt to repair the disc. However, this attempted reparative process further exposes the disc to increasing inflammatory mediators. ^{8,10,11, 15,16,19} The inflammatory mediators interact in a complex way to induce, enhance and propagate persistent pain. ¹⁹ Eventually, the degradative cascade causes the native cells to undergo phenotypic changes, senescence and apoptosis, which further reduces any anabolic capability of the disc. ^{8,10,11, 15,16}

The resultant low back pain from disc degeneration represents a substantial social and economic burden to the community as well as adding to one's long-term physical disability and reduced quality of life. It is estimated that as much as 80% of the analysis set experiences at least one significant episode of low back pain during life and approximately 2.5% of the working analysis set will take some sick leave during the year as a result of low back pain. The direct costs of low back pain in modern western countries has been estimated at billions of dollars, most of which is spent on consulting general practitioners, physical therapists and other conservative practitioners. ^{20,21} Total indirect expenditure, including surgical management, may be ten times higher. ²²

